8.3 Recording of adverse events

If the patient has experienced adverse event(s), the investigator will record the following information in the CRF:

The **nature of the event**(s) will be described by the investigator in precise standard medical terminology (i.e. not necessarily the exact words used by the patient).

The **duration of the event** will be described in terms of event onset date and event ended data. The **intensity** of the adverse event will be categorised as mild / moderate / severe / life-

threatening / death according to Common Terminology Criteria for Adverse Events version 4.0:

- Mild: asymptomatic or mild symptoms; clinical or diagnostic observations only; intervention not indicated;
- Moderate; minimal, local or non-invasive intervention indicated; limiting age-appropriate instrumental activities of daily life;
- Severe: Severe or medically significant but not immediately life-threatening; hospitalisation or prolongation of hospitalisation indicated; disabling; limiting self-care activities of daily life;
- Life-threatening consequences: urgent intervention indicated.

The **causal relationship** of the event to the study medication will be assessed as one of the following:

- Unrelated: There is not a temporal relationship to investigational product administration (too early, or late, or investigational product not taken), or there is a reasonable causal relationship between non-investigational product, concurrent disease, or circumstance and the AE.
- Unlikely: There is a temporal relationship to investigational product administration, but there is not a reasonable causal relationship between the investigational product and the AE.
- Possible: There is reasonable causal relationship between the investigational product and the AE. Dechallenge information is lacking or unclear.
- Probable: There is a reasonable causal relationship between the investigational product and the AE. The event responds to dechallenge. Rechallenge is not required.

Definite: There is a reasonable causal relationship between the investigational product and the AE. Action taken: Which investigations/medical procedures/treatments that are initiated as a result of the adverse event.

The **outcome** of the adverse event – whether the event is resolved or still ongoing.

It is important to distinguish between seriousness and severity of AEs. Severity is a measure of intensity whereas seriousness is defined by the criteria in Section 8.1. An AE of severe intensity need not necessarily be considered serious. For example, nausea that persists for several hours may be considered severe nausea, but is not an SAE. On the other hand, a stroke that results in only a limited degree of disability may be considered a mild stroke, but would be an SAE.

8.4 Reporting procedure

8.4.1 Adverse events, adverse events of special interest and serious adverse events

All adverse events and serious adverse events that should be reported as defined in section 8.1.1 will be recorded in the patient's CRF. SAEs must be reported by the investigator to the sponsor, Oslo University Hospital, within 24 hours after the site has gained knowledge of the SAE. The Serious Adverse Event Report Form must be completed, documented in the eCRF, signed and sent to [name]. The initial report shall promptly be followed by detailed, written reports if necessary. The initial and follow-up reports shall identify the trial subjects by unique trial code numbers assigned to the latter. The sponsor keeps detailed records of all SAEs reported by the investigators and performs an evaluation with respect to seriousness, causality and expectedness

8.4.2 Suspected unexpected serious adverse reactions

SUSARs will be reported to the National Competent Authorities in each participating country and the local Ethics Committee according to national regulations. The following timelines should be followed:

The sponsor will ensure that all relevant information about suspected serious unexpected adverse reactions that are fatal or life-threatening is recorded and reported as soon as possible to the Norwegian Medicines Agency and the Regional Committee for Medical and Health Research Ethics in any case no later than seven (7) days after knowledge by the sponsor of such a case, and that relevant follow-up information is subsequently communicated within an additional eight (8) days. The sponsor shall ensure that suspected adverse reactions that are serious and unexpected are reported to the Norwegian Medicines Agency and the Regional Committee for Medical and Health Research Ethics within 15 days of the sponsor after knowledge of the event. The sponsor shall inform all investigators of the trial substance in question of suspected adverse reactions that are serious and unexpected. An account of any interruption in treatment or any breaking of the treatment code, the investigator's assessment of the causal relationship, and consequences for further testing shall accompany the notification of suspected adverse reactions pursuant to the first and second paragraphs. SUSARs will be reported to the drug manufacturer, Amgen[®] at time of regulatory submission.

The National Competent Authorities may require that individual reports of adverse events described in collective reports should also be submitted. The sponsor shall keep detailed records of all adverse events that are reported to him by the investigator. The records shall be submitted to the National Competent Authorities on request. Amgen[®] will receive annual safety reports and a Final (End of Study) Report, including unblinded data for blinded studies and reports of unauthorised use of a marketed product.

8.4.3 Annual safety report

Once a year throughout the clinical trial, the sponsor will provide the Norwegian Medicines Agency with an annual safety report. The format will comply with national requirements.

8.4.4 Clinical study report

The adverse events and serious adverse events occurring during the study will be discussed in the safety evaluation part of the Clinical Study Report.

8.5 Procedures in case of emergency

The investigator is responsible for assuring that there are procedures and expertise available to cope with emergencies during the study (see also section 10.2.3).

8.6 Safety monitoring

A data safety monitoring committee will be appointed to assess trial safety. The committee consist of an independent clinician and a statistician. It will receive reports summarising patient recruitment and the number of AEs / SAEs after the first 20 patients have been randomised, and again after 50 % and 100 % of patient enrolment. The data safety monitoring committee will receive additional information on demand and can advise temporary or permanent stop in patient enrolment. The committee will have access to the randomisation code, and can, if they so choose, perform an interim analysis regarding the number of adverse events and serious adverse events. The data safety monitoring committee is independent from the sponsor and will be composed of individuals with no competing interest with regard to the study investigational products or study outcome.

9 Data management and monitoring

9.1 Electronic case report forms (eCRFs)

The designated investigator staff will enter the data required by the protocol into the electronic Case report form (eCRF). The Principal Investigator is responsible for assuring that data entered into the eCRF are complete, accurate, and that entry is performed in a timely manner. If any assessments are omitted, the reason for such omissions will be noted in the eCRFs. Corrections, with the reason for the corrections will also be recorded. After database lock, the investigator will receive a digital copy of the subject data for archiving at the investigational site. An online eCRF will be used in this trial.

9.2 Source data

Some data will be recorded directly into the eCRF, which, together with the patient medical record, is to be considered the source data. All data important for patient safety and continued care must be duplicated in the patient's medical record as described below. Study-specific imaging data and blood analyses are independent source data.

The medical records of each patient should clearly describe at least:

- That the patient is participating in the study
- The patient's study identification number
- Date when the informed consent was obtained from the patient;
- Results of all assessments confirming a patient's eligibility for the study;
- Diseases (past and current; both the disease studied and others, as relevant);
- Surgical history, as relevant;
- Treatments withdrawn/withheld due to participation in the study;
- Results of assessments performed during the study;
- Treatments provided, changes in treatments during the study and the time points for the changes;
- Visits to the clinic / telephone contacts during the study, including those for study purposes only;
- Non-Serious Adverse Events and Serious Adverse Events (if any) including causality assessments;
- Date of, and reason for, discontinuation from study treatment;
- Date of, and reason for, withdrawal from study;
- Date of death and cause of death, if available.

9.3 Study monitoring

The investigator will be visited on a regular basis by the Clinical Study Monitor, who will check that the study is conducted as approved by the Ethics committee and adheres to GCP guidelines.

Sponsor's representatives (e.g. monitors, auditors) and/or competent authorities will be allowed access to source data for source data verification in which case a review of those parts of the hospital records relevant to the study may be required.

9.4 Confidentiality

The investigator shall arrange for the secure retention of the patient identification and the code list. Patient files shall be kept for the maximum period of time permitted by each hospital. The study documentation (CRFs, Site File etc.) shall be retained and stored during the study and for 15 years after study closure. All information concerning the study will be stored in a safe place inaccessible to unauthorised personnel.

9.5 Database management

Data will be entered into the eCRF without delay and stored in the dedicated and secured online platform (Viedoc[®]). Data will be extracted from Viedoc for analysis, and the extracted data will be

stored in dedicated, secure areas at the participating centres. Data will be stored in a de-identified manner, where each study participant is recognisable by his/her unique trial subject number. The data will be stored until Dec 31st, 2040 in compliance with local regulations, or until the patient requires that his/her data are deleted. Data in the eCRF will be handled according to GCP. Only the personnel authorised to enter and/or analyse data (i.e. investigators) will have access to the database.

9.6 Biobanking

A biobank will be established at the Dept. of Cardiology, Oslo University Hospital, Rikshospitalet for the analysis of serum and plasma. The samples will be stored in multiple aliquots and labelled with the unique trial subject number, and the letter A signifying baseline, and the letter B signifying the visit at one month, C signifying 2 months etc. The samples will be stored at -80 degrees Celsius in a dedicated research freezer. The material is scheduled for destruction by Dec 31st, 2040. [name] at Oslo University Hospital, Rikshospitalet will be responsible for the biobank. Biochemical analyses may be performed at other participating centres, and the samples may be shipped between countries for storage and analyses.

10 Statistical methods and data analysis

10.1 Determination of sample size

This trial is designed to assess the effect of evolocumab on intima thickness as measured by coronary IVUS. The sample size of the present study is based calculations relating to the primary outcome, the change in maximal intima thickness from baseline to one year. In the SCHEDULE trial, we observed an increase in the maximal intima thickness of 0.08 +/- 0.12 mm in the placebo group, whereas the corresponding increase was 0.03 +/- 0.06 mm in the everolimus arm.²¹ Intensive cholesterol reduction has been shown to actually reverse the atherosclerotic volume in previous trials. We therefore hope to achieve a 0.05 mm between-group difference in the change in the intima thickness in the EVOLVD trial. With an estimated 0.09 mm standard deviation, we will require 51 patients in each arm with a power of 80%, at a two sided alpha level of 5%. To increase the chances of reaching the primary and secondary outcomes, and to compensate for uncertainties in this calculation, we will ensure that 120 patients complete the one-year follow-up. To allow for a dropout rate of 5 - 10% we aim to include 130 patients.

In the SCHEDULE trial, the mean increase in the percent atheroma volume was 1.3 ± 2.3 percentage points in the everolimus arm versus 4.2 ± 5.0 percentage points in the cyclosporine group. Provided that evolocumab can produce a similar reduction in the progression of the atheroma volume, with an estimated standard deviation of 3.7 percentage points, we will need just 26 patients in each arm to detect a between-group difference in the important secondary outcome, the change in percent atheroma volume, with an α of 5 % and a power of 0.8.

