This trial is designed to assess the effect of evolocumab on intima thickness as measured by coronary IVUS. The sample size of the present study is based calculations relating to the primary outcome, the change in maximal intima thickness from baseline to one year. In the SCHEDULE trial, we observed an increase in the maximal intima thickness of 0.08 (SD 0.12) mm in the placebo group, whereas the corresponding increase was 0.03 (SD 0.06) mm in the everolimus arm.² Intensive cholesterol reduction has been shown to actually reverse the atherosclerotic volume in previous trials.³,⁴ We therefore hope to achieve a 0.05 mm between-group difference in the change in the intima thickness in the EVOLVD trial. With an estimated 0.09 mm standard deviation, we will require 51 patients in each arm with a power of 80%, at a two-sided alpha level of 5%. To increase the chances of reaching the primary and secondary outcomes, and to compensate for uncertainties in

this calculation, we will aim for 120 patients to complete the one-year follow-up. To allow for a dropout rate of 5 - 10%, we plan to include 130 patients.

9 General Considerations

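### Is 51 patients per arm too few because the planning SD of 0.09 mm does not visibly follow from the quoted arm SDs of 0.12 and 0.06 mm?

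*Protocol*

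**What the plan says.** Protocol 10.1 bases the sample size on the change in maximal intima thickness over one year. From the earlier everolimus trial it takes "an increase in the maximal intima thickness of 0.08 +/- 0.12 mm in the placebo group" and reports that "the corresponding increase was 0.03 +/- 0.06 mm in the everolimus arm". SAP 8 repeats the figures and labels them as standard deviations: "an increase in the maximal intima thickness of 0.08 (SD 0.12) mm in the placebo group" and "the corresponding increase was 0.03 (SD 0.06) mm in the everolimus arm". Both sections hope for a between-arm difference of 0.05 mm and then say "With an estimated 0.09 mm standard deviation, we will require 51 patients in each arm with a power of 80" per cent, at two-sided 5%.

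Neither section stops at 51. The protocol goes on: "to compensate for uncertainties in this calculation, we will ensure that 120 patients complete the one-year follow-up", and then "To allow for a dropout rate of 5 - 10% we aim to include 130 patients". The SAP has the same two steps, but treats 120 completers as an aim rather than something to be ensured.

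Protocol 10.1 handles the secondary outcome, percent atheroma volume, in the same way. It quotes SDs of 2.3 and 5.0 percentage points and concludes that "with an estimated standard deviation of 3.7 percentage points, we will need just 26 patients in each arm".

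The primary analysis is ANCOVA adjusted for baseline (Protocol 10.5) and for baseline and centre (SAP 11.2).

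**The concern.** The two quoted SDs differ by a factor of two, and the planning SD lies exactly midway between them. Averaging SDs is not how variances combine. For two arms of equal size, the standard error of a difference in mean change depends on the average of the two variances, so the matching single SD is the root mean square, which is larger than 0.09 mm. If 0.09 came from simple averaging, 51 per arm is too low for 80% power under the plan's own inputs.

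The increase from 51 to 60 per arm is also presented as a margin for uncertainty. If part of it only makes good a low SD, the margin is thinner than a reader would think. Patients without adequate scans at both visits fall outside the full analysis set (SAP 9.2.1), and neither sample size section allows for them separately.

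**Working it through.** **Inputs.** Difference 0.05 mm; arm SDs 0.12 and 0.06 mm; planning SD 0.09 mm; two-sided 5%; power 80%; 120 completers; 130 enrolled; dropout 5 to 10% (Protocol 10.1, SAP 8). Allocation 1:1 (Protocol 3).

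**1. The plan's own figure.** n per arm = 2 × (1.960 + 0.842)² × (SD/0.05)² = 15.70 × (SD/0.05)².
- SD 0.09: 15.70 × 3.24 = 50.86, so 51. The stated figure reproduces. The exact t-test version gives 52.

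**2. Both quoted SDs carried over, change scores compared.**
- Root mean square: √((0.12² + 0.06²)/2) = √0.009 = 0.0949 mm.
- n per arm: 15.70 × 0.009/0.0025 = 56.51, so 57 (58 by t-test).

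| Patients | t-test power, SD 0.0949 |
|---|---|
| 51 per arm | 75.0% |
| 60 per arm | 81.7% |
| 117 in total (130 × 0.90) | 80.7% |
| 123 in total (130 × 0.95 = 123.5) | 82.6% |

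With SD 0.09, power at 60 per arm is 85.5%.

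**3. Rounding.** The quoted SDs have two decimals.
- Low edge, 0.115 and 0.055: root mean square 0.0901, n = 51.02, so 52; power 85.4% at 60 per arm.
- High edge, 0.125 and 0.065: root mean square 0.0996, n = 62.32, so 63 (64 by t-test); power 77.8% at 60 per arm.

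At the low edge the root mean square is itself 0.09 to the precision given.

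**4. Could 0.09 be a pooled SD?** Let w be the share of the earlier trial's patients in its control arm. The documents do not give it, so w is an assumption.
- Intima thickness: w = (0.09² − 0.06²)/(0.12² − 0.06²) = 0.0045/0.0108 = 0.417.
- Atheroma volume: w = (3.7² − 2.3²)/(5.0² − 2.3²) = 8.40/19.71 = 0.426.
- A single w = 0.42 gives 0.0902 mm and 3.68 points, which round to both planning values.

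Simple averages (0.09 and 3.65) fit about as well. The equal-weight root mean squares of the quoted SDs (0.0949 and 3.89) reproduce neither planning value.

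**5. The planned analysis.** Under ANCOVA the variance of the change is multiplied by 1 − r², where r is the correlation between baseline and change. The documents give no r, so these are assumed values.
- r = 0.2: 56.51 × 0.96 = 54.3, so 55 per arm.
- r = 0.32: 56.51 × 0.898 = 50.7, so 51 per arm.
- r = 0.5: 56.51 × 0.75 = 42.4, so 43 per arm.

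**6. Atheroma volume.** Root mean square √((5.0² + 2.3²)/2) = 3.89; difference 4.2 − 1.3 = 2.9. This gives n = 28.27, so 29 (30 by t-test) instead of 26. Power at 60 per arm is 98.2%.

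**The case for a change.** The best case for acting is that the gap is real and cheap to close. The step from 0.12 and 0.06 to 0.09 is missing from both documents, and the same kind of step is missing for atheroma volume. The sample size text claims no gain from ANCOVA and gives no correlation, so that gain cannot be credited to the authors. On the central figures, 6 to 7 of the 9 patients per arm added between 51 and 60 only restore 80% power. By t-test, 80% on the quoted SDs needs 2 × 58 = 116 analysable patients, so 130 can absorb 14 losses of any kind (14/130 = 10.8%). With SD 0.09 it needs 2 × 52 = 104, leaving room for 26 (20%). Ten per cent dropout already takes 13, before any inadequate scan is counted.

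What stands is the observation that the derivation is missing and that the margin is thinner if both quoted SDs apply. What does not stand is that 51 is an error. It follows correctly from an SD labelled as an estimate, and that SD has at least one legitimate origin. The root mean square also needs evolocumab patients to show the small spread of the everolimus arm. The plan borrows the 0.05 mm difference from that trial; it does not say that each arm's SD carries over.

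The loss to inadequate scans cannot be sized from the documents. Protocol 7.1.1 accepts an early second scan after at least six months of treatment, which may offset some of the dropout. Explaining where 0.09 came from would not change that loss.

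**Conclusion.** No change to the plan. The missing derivation is a reporting gap of the lowest order. The stated 51 per arm is correct for SD 0.09 mm. The alternative of 57 to 58 (52 to 64 over rounding and choice of formula) rests on three assumptions: both quoted SDs carry over unchanged, the arms are equal in size, and the test is on change scores. The planned test is ANCOVA, so the third does not describe this trial's primary analysis.

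Even with all three granted, the number the trial works to is 60 completers per arm. That gives 81.7% power, and 80.7% if dropout reaches the planned maximum of 10%. Power falls below 80% at 60 per arm only towards the upper rounding edge (77.8%), before any gain from baseline adjustment. The plan adds patients expressly because the calculation is uncertain, and uncertainty in the SD is of that kind.

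Nothing would be gained by rewriting. Enrolment, analysis and decision rule would all stay as they are. A protocol amendment needs regulatory and ethics approval (Protocol 11.3), recruitment was due to end in February 2022 (Protocol 3), and SAP 7.4 already describes randomisation in the past tense. The protocol's firmer wording on 120 completers is a matter of phrasing that the SAP has already softened, and atheroma volume is amply powered on either SD.

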10.2 Randomisation

10.2.1 Allocation- sequence generation

Balanced, permuted block randomisation (in a 1:1: ratio for the two study arms) will be performed online in Viedoc and stratified by centre.

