9.2 Populations for analysis

9.2.1 Full analysis set (modified intention-to-treat population)

The full analysis set (FAS) will include all patients who were randomised and who (irrespective of receipt of actual treatment) had intracoronary ultrasound adequate for the determination of coronary intima thickness at baseline and at the 12 months follow-up. The adequacy of the ultrasound examination must be determined before database lock and the randomisation code is opened. The primary analysis of the primary endpoint (and all secondary endpoints) will be carried out on the FAS.

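### Enrolling 130 yields the stated 120 completers only up to 7.7% dropout, and 117 at the plan's own 10%; power stays near 85%, so this is a small error to correct in wording

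*Protocol*

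**What the plan says.** Protocol 10.1 builds the sample size in three steps.

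- **Calculated need.** The target effect is given as "We therefore hope to achieve a 0.05 mm between-group difference in the change in the intima thickness in the EVOLVD trial". For 80% power and a two-sided alpha of 5%, the protocol concludes: "With an estimated 0.09 mm standard deviation, we will require 51 patients in each arm". That is 102 in total.
- **Completer target.** To improve the chances on the primary and secondary outcomes and to cover uncertainty in the calculation, the protocol states "we will ensure that 120 patients complete the one-year follow-up".
- **Enrolment.** "To allow for a dropout rate of 5 - 10% we aim to include 130 patients".

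SAP section 8 repeats the calculation and the enrolment figure ("To allow for a dropout rate of 5 - 10%, we plan to include 130 patients"), but says the trial will aim for 120 completers where the protocol says it will ensure them.

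SAP 9.2.1 defines the set for the primary analysis. The full analysis set (FAS) consists of randomised patients who "had intracoronary ultrasound adequate for the determination of coronary intima thickness at baseline and at the 12 months follow-up". SAP 9.4 adds that the primary analysis imputes nothing. Neither sample-size section gives a rate of inadequate or unmatched scans.

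**The concern.** A plan that names a completer target, a dropout range and an enrolment figure should have the three agree across the range. Here they do not at the upper end, because a 10% loss from 130 leaves fewer than 120.

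There is also a difference in what is counted. The allowance concerns patients who complete follow-up, while the primary analysis needs two adequate IVUS recordings that can be matched. A patient can attend the 12-month visit and still fall outside the FAS. Protocol 7.1.1 has the core laboratory read the scans only after trial closure, so it cannot screen out a poor baseline recording before randomisation.

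The figure of 120 is the plan's stated margin over the calculated 102. A reader may take it as the number that will be analysed, and so expect somewhat more power than the plan delivers at the top of its own dropout range.

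**Working it through.** **Inputs.** Difference 0.05 mm, SD 0.09 mm, two-sided alpha 5%, power 80%, 51 per arm, target 120, dropout 5-10%, enrolment 130 (all Protocol 10.1); 1:1 allocation (Protocol 10.2.1). The rate of unusable scan pairs is not given in either document.

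**1. Reproduce the plan's calculation.** Normal approximation, n per arm = 2 × (z₀.₉₇₅ + z₀.₈₀)² × (SD/difference)²
= 2 × (1.960 + 0.842)² × (0.09/0.05)² = 50.9, so 51 per arm and 102 in total. This matches. The two-sample t-test gives 51.8, so 52 per arm and 104 in total.

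**2. Enrolment needed for 120 completers**, 120/(1 − d), and completers left from 130, 130 × (1 − d):

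| Dropout d | Enrolment needed for 120 | Completers from 130 |
|---|---|---|
| 5% | 126.3 → 127 | 123.5 |
| 7.5% (midpoint) | 129.7 → 130 | 120.25 |
| 7.7% (10/130) | 130 | 120 |
| 10% | 133.3 → 134 | 117 |

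So 130 is the right inflation for the midpoint of the range. It falls short only above 7.7%, by at most 120 − 117 = 3 patients.

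**3. Power at the resulting sizes** (0.05 mm, SD 0.09 mm, equal arms):

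| Analysed, total | Normal approximation | Two-sample t-test |
|---|---|---|
| 120 | 86.1% | 85.5% |
| 117 | 85.2% | 84.6% |
| 104 | 80.9% | 80.1% |
| 102 | 80.1% | 79.3% |

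Going from 120 to 117 costs about 0.9 percentage points by either method.

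**4. Total loss that keeps 80% power.** Loss here means dropout plus unusable scan pairs.
- Normal approximation: 130 − 102 = 28, and 28/130 = 21.5%.
- Two-sample t-test: 130 − 104 = 26, and 26/130 = 20.0%.

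**5. Room for unusable pairs at 10% dropout** (117 completers).
- Normal approximation: 1 − 102/117 = 12.8% of completers.
- Two-sample t-test: 1 − 104/117 = 11.1% of completers.

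**6. Range under assumed rates.** These rates are assumptions, since the documents give none. Dropout is held at 10%:

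| Assumed share of completers without a usable pair | Pairs analysed | Power, normal | Power, t-test |
|---|---|---|---|
| 5% | 111.1 | 83.4% | 82.7% |
| 10% | 105.3 | 81.3% | 80.6% |
| 15% | 99.5 | 79.1% | 78.3% |
| 20% | 93.6 | 76.7% | 75.8% |

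At 5% dropout with 15% unusable, 105.0 pairs remain (81.2% normal, 80.5% t-test).

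**The case against.** The defence is strong on consequence.

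- **130 is a reasonable single figure for the range.** It is the exact inflation at 7.5% and leaves 123.5 at 5%. This stands, and it rules out saying that 130 fails across 5-10%. The mismatch is confined to 7.7-10%.
- **The planned property is power of 80% at 102, and 117 exceeds it.** This stands. The 18-patient margin (120 − 102) is there for uncertainties, and unusable scans can be charged to it even though they are not itemised.
- **The SAP only aims for 120.** It does soften the protocol's promise, but it repeats the same range and the same 130, so the arithmetic mismatch remains.
- **Several provisions limit the loss.** Contraindication to angiography with IVUS bars entry. Baseline assessments precede randomisation. Patients who stop study drug stay in follow-up. Protocol 7.1.1 allows an early second IVUS after at least 6 months of treatment. These help, although the FAS wording refers to the 12-month follow-up, so it is unclear whether an early scan counts.
- **The power figures are, if anything, conservative.** They describe a comparison of change scores, whereas SAP 11.2 plans ANCOVA with baseline and centre. Apart from a few degrees of freedom for centre, baseline adjustment does not increase the residual variance in large samples. This stands.
- **The SAP already plans to report the outcome.** The number analysable for the primary endpoint, dropout by arm and sensitivity analyses for missing primary data are all there. That covers reporting but does not correct the planning statement.

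A reader might infer that the trial is underpowered because scan failures have no separate allowance. The documents do not support this. Power falls below 80% only under rates such as the assumed 15% or 20% at 10% dropout, and nothing in the protocol or SAP makes such rates likely or unlikely.

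**Conclusion.** The point holds as a small arithmetic error. Enrolling 130 supports the 120-completer statement up to 7.7% dropout and misses it by up to 3 patients between there and 10%. Power at 117 is 84.6% to 85.2% depending on method, so the planned 80% is not threatened by the stated dropout alone.

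The difference between completers and the FAS is a clarification, not a demonstrated loss. The plan does not say how many analysable pairs it expects, and the documents give no rate from which to work it out. What can be said is conditional: 80% power is kept while total loss is at most 21.5% (normal approximation) or 20.0% (two-sample t-test). Both limits assume 0.05 mm, SD 0.09 mm, near-equal arms and an unadjusted comparison of changes.

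**What to change.** Amend the wording in Protocol 10.1 and SAP section 8, in the same terms, to say:

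- 130 randomised leaves about 117 to 123 completers at 5-10% dropout;
- the planned 80% power for 0.05 mm with SD 0.09 mm is kept while enough analysable IVUS pairs remain. State one threshold and name its method: at least 102 pairs by the normal approximation already used (total loss up to 28/130 = 21.5%), or at least 104 by a two-sample t-test (total loss up to 26/130 = 20.0%);
- total loss means dropout together with inadequate or unmatched scans, so that the statement refers to the FAS of SAP 9.2.1.

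The threshold and any quoted power should come from the same method. At 102 pairs the t-test gives 79.3%, so mixing the two would introduce a new inconsistency.

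The cost is wording only, with no added patients and no change to the analysis. The one downside is that the stated completer figure becomes slightly less favourable.
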